1.1 Phase and Design of the Clinical Study

This is a prospective, multicenter, single arm, non-randomized Phase 2 study to evaluate safety and efficacy of Humacyte's Human Acellular Vessel (HAV) for use as a vascular prosthesis for femoro-popliteal bypass in patients with peripheral arterial disease (PAD).

1.2 Investigator(s) and Study Center(s)

Up to 8 sites in the USA.

1.3 Visit Terminology

Notation used in eCRF and protocol	Notation used for table, listing and graph presentation	Notification for treatment phases
Visit 1 (Screening, Day -35 to -1)	Screening	Screening
Visit 2 (Day 1)	Day 1	HAV implantation
	Baseline ¹	
Visit 3 (Day 5)	Day 5	Follow-up
Visit 4 (Day 29), ± 4 days	Day 29	
Visit 5 (Month 3), ± 14 days	Month 3	
Visit 6 (Month 6), ± 14 days	Month 6	7
Visit 7 (Month 9), ± 14 days	Month 9	7
Visit 8 (Month 12/ET), ± 14 days	Month 12	
Unscheduled	Unscheduled	
Every 6 - 12 months through Month 60 (± 30 days) at "standard of care" clinic visits	SOC Visit 1 to 10	Additional follow up

¹ The closest non-missing value prior to surgery on Day 1 will be used as baseline value. ET = Early Termination

1.4 Objectives

1.4.1 Primary Objectives:

This is an open label Phase 2 study. There is no formal hypothesis testing.

Statistical Analysis Plan	
CLN-PRO-004	

Final Analysis 8/23

Safety:

• To evaluate the safety and tolerability of the Humacyte HAV in PAD patients undergoing femoro-popliteal bypass surgery

Efficacy:

- To determine the patency (primary, primary assisted and secondary) rate of the Humacyte HAV at Month 12
- To determine the incidence of hemodynamically significant stenosis (>70%) defined by duplex ultrasound, and the time to stenosis development

1.4.2 Secondary Objectives:

Safety:

- To assess changes in the panel reactive antibodies (PRA) response after HAV implantation
- To determine mechanical stability of the HAV based on freedom from aneurysmal degeneration on duplex ultrasound and computed tomography (CT) imaging
- To determine HAV durability in terms of freedom from need for HAV explanation or replacement due to infection, bleeding or conduit degeneration

Efficacy:

- To determine the patency of the HAV (primary, primary assisted and secondary) at Months 3, 6 and 9
- To determine the rates of interventions needed to maintain / restore patency in the HAV through Month 12
- To assess effect of HAV implantation on symptoms of PAD using the VascuQol instrument
- To assess effect of the HAV on ankle-brachial index (ABI)
- To assess effect of the HAV on 6 minute walk test

1.5 Sample Size Estimation

Up to 25 patients were planned, and 15 patients were recruited into the study. As this Phase 2 study is one of the first studies of the HAV in humans with PAD, the number of patients was chosen in order to provide preliminary evidence of safety and efficacy of the HAV to allow the initiation of further trials in larger numbers of patients.

The study is not powered to assess the efficacy of the HAV.

2 Efficacy and Safety Variables

2.1 Primary Safety Endpoints

Final Analysis 9/23

- Incidence of HAV aneurysm formation (true or pseudo)
- Anastomotic bleeding or spontaneous rupture
- HAV infection
- HAV removal
- Significant local inflammation at the HAV implantation site
- Frequency and severity of adverse events (AEs)

2.2 Secondary Safety Endpoints

- Change from baseline in PRA
- Change from baseline in hematology, coagulation, and clinical chemistry parameters

2.3 Primary Efficacy Endpoints

- HAV patency rates (primary, primary assisted, and secondary patency)
- Hemodynamically significant stenosis (>70% by duplex ultrasound criteria)

2.4 Secondary Efficacy Endpoints

- HAV interventions
- Patient reported PAD symptoms (VascuQol)
- ABI
- 6 minute walk test
- HAV remodeling at Months 1 (Day 29), 6 and 12 by CT angiography and ultrasound (US)

2.5 Long Term Endpoints (Post Month 12 through Month 60)

- HAV interventions
- Evidence of aneurysmal dilatation or stenosis of the HAV on routine clinical duplex US
- Primary, primary assisted, and secondary patency at 18, 24, 30, 36, 42, 48, 54 and 60 months
- Limb salvage/amputation at 18, 24, 36, 48, and 60 months, for all subjects who have not died, withdrawn, or been lost to follow-up.
- Incidence of surgical revascularization of the implanted limb, at the level of the HAV or distal to HAV, for all patients who have not died, withdrawn, or been lost to follow-up.

Statistical Analysis Plan	
CLN-PRO-004	

Final Analysis 10/23

 VascuQol PAD symptom assessment consists of 25 questions. The total score and the 5 domain scores (Activity, Symptom, Pain, Emotional, and Social) will be recorded in the clinical database, at 18, 24, 36, 48 and 60 months, for all patients who have not died, withdrawn, or been lost to follow-up.

2.6 Other Efficacy Variables

- Doppler ultrasound and high resolution ultrasound
- Time to loss of patency

2.7 Other Relevant Variables

- Medical history
- Smoking history
- 12-lead electrocardiogram (ECG)
- Pregnancy test
- Prior and concomitant medication
- HAV implantation and angiography/intraop ultrasound
- Documentation of surgery
- Study termination and premature discontinuation

3 Statistical Analysis Set

One analysis population set will be analyzed.

3.1 Safety Analysis Set

The safety analysis set (SAF) consists of all enrolled patients who received an HAV when the final patient enrolled reaches 12 months post-implant. For discontinued or withdrawn patients, all available data will be included in the safety analyses.

3.2 Additional Subgroup Analysis

Where appropriate, subgroup analysis may be performed for the main efficacy parameters if enough patients within the subgroups allow further insight to the data.

3.3 Assignment of Analysis Set to Analysis

All analyses will be based on SAF.

3.4 Interim Analysis

Data Monitoring Committee (DMC) reports will be provided during the course of the study.

Statistical Analysis Plan	Final Analysis
CLN-PRO-004	11/23

Endpoints will be assessed over a period of up to 60 months after HAV implantation.

- The **primary analysis** of the study will be based conducted on the earlier of a) when the final patient enrolled reaches 12 months post-implant or b) all subjects enrolled in the initial 36 month accrual period have reached 12 months post-implant. The SAP will call this the 1-year analysis.
- The **final analysis** will occur at the end of the study, when all patients have completed or exited the study.

The database extraction for the **1-year analysis** will include all study data collected at the time of the database extraction. The by-visit tables and figures will display all time points present in the data, including visits after the Month 12 visit (where applicable). Event tables (such as concomitant medications, AEs), will include all events during the study. Listings will display all study data available, including data collected after the Month 12 visit.

The database for the final analysis will include all study data and by-visit tables will display all study timepoints.

4 Statistical Evaluation

All tables, figures and listings will be produced using SAS (v9.4 or a more recent version).

Unless otherwise stated, categorical data will be presented using counts and percentages, whilst continuous parameters will be summarized using standard summary statistics as appropriate (n, mean, standard deviation [SD], median, minimum, maximum, 25th percentile, and 75th percentile). Minima and maxima will be quoted to the number of decimal places as recorded in the case report form (CRF); means, SDs and medians will be quoted to one further decimal place.

The closest non-missing values prior to implantation on Day 1 will be used as baseline values.

Unless otherwise stated, all confidence intervals will be presented as 95% two-sided intervals. For categorical endpoints, if all values are either success or failure, the exact CI will be presented.

As no sample size assessment has been undertaken, all analysis results are considered to be exploratory.

Details on the specification, definition, calculation and analysis of the efficacy and safety endpoint variables are given in Section 2 and the following sections.

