# 4.3. Duration of Study Participation

For an individual subject, the expected duration of active study participation is approximately 61 months. Enrollment (accrual) is expected to occur over 36 months. Additional data on patient and HAV status will be collected at 6 month intervals through 60 months after HAV implantation.

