# 8.2. Serious Adverse Event Definition

An AE is considered "serious" if, in the view of either the investigator or Sponsor, it:

- Results in death
- Is life-threatening
  - The term "life-threatening" in the definition of "serious" refers to an event in which the patient was at immediate risk of death at the time of the event; it does not include an adverse event that had it occurred in a more severe form, might have caused death.

- Requires patient hospitalization or prolongation of existing hospitalization
  - This is defined as the patient being hospitalized for 24 hours or more or the patient's hospital stay being prolonged for at least an additional overnight stay.
- Requires intervention to prevent permanent damage
- Results in persistent or significant disability/incapacity
- Is a congenital anomaly/birth defect
- Important Medical Events
  - For the purpose of this study, this includes any event involving the HAV that results in a surgical or endovascular radiological intervention. The event(s) which caused the procedure should be reported as an SAE. For example: in the event of HAV thrombosis, the thrombosis would be considered the SAE; any associated stenoses (or other associated findings) that are present would be considered AEs.

Medical and scientific judgment should be exercised in deciding whether expedited reporting to the sponsor is appropriate in other situations, such as important medical events that may not be immediately life-threatening or result in death or hospitalization but may jeopardize the patient or may require medical or surgical intervention to prevent one of the other outcomes listed in the definition above. These may also be considered to be SAEs.

Note: Hospitalization for the surgery to implant the HAV is not a SAE. However, prolongation of the initial hospitalization due to an AE will be considered a SAE.

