#### 8.4. Events of Special Interest

Events of Special Interest are:

- HAV occlusion (thrombosis)
- HAV spontaneous rupture

- latrogenic injuries are not an Event of Special Interest and should be reported as an AE
- HAV infection
- HAV abandonment
- HAV aneurysm
- HAV pseudoaneurysm
- HAV excision (partial or complete)

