# 8.5. Reporting of Adverse Events

At each evaluation, the investigator will determine whether any AEs have occurred. The patient will be questioned in a general way and no specific symptoms will be suggested. If any AEs have occurred, they should be documented in the patient's medical chart and recorded on the AE pages of the eCRF. If known, the diagnosis should be recorded in preference to the listing of individual signs and symptoms. All serious adverse events (SAEs should be reported to the Safety Contract Research Organization (CRO) within 24 hours from the time the investigator or study personnel first become aware of the event.

AE reporting begins from implantation of the HAV (the moment the patient undergoes anesthesia) and ends at the conclusion of the Month 12 or ET visit unless an unresolved AE is still being followed.

During the long term follow up period from post Month 12 through Month 60, only the following will be reported by the investigator:

- All SAEs
- All Events of Special Interest (Section 8.4)

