The assignment to a patency (yes/no) (primary, primary assisted, secondary patency) will be verified during the Data Review Meeting (DRM) using all data of CRF sections referring to HAV patency, clinical examination of the HAV site, doppler ultrasound assessment of HAV patency, HAV intervention, premature discontinuation, and AEs.

Patency rates will be presented with frequency tabulations showing patient numbers and patency rates for Month 12.

Clopper-Pearson confidence intervals (CI) will be presented for frequency counts of patency rates.

Kaplan-Meier (K-M) curves for primary, primary assisted, and secondary patency will be created at the 1-year report and for all subsequent reports. K-M curves will be provided using two censoring methods:

- a. Patients who die, withdraw from the study, or are lost to follow-up are censored at the day of the respective event.
- b. Patients who die, withdraw from the study, or are lost to follow-up are considered as having suffered failure of secondary patency at the day of the respective event.

Efficacy Objective #2:

Hemodynamically significant stenosis (>70% by duplex ultrasound criteria): The duplex ultrasound parameters will be summarized by planned visit up to Month 12.

- Frequency of stenosis occurrence, location of stenosis, and presence of aneurysm.
- Numeric summary of volumetric flow rate and inner diameter of HAV mid bypass.

A stenosis event can occur between planned study visits (i.e. Unscheduled Visits). A "by visit"

Statistical Analysis Plan	
CLN-PRO-004	

summary will represent the stenosis event/information that occurred before or on the planned visit. For example, the summary at Day 5 will denote the number of patients who had stenosis occur up to Day 5 or on the Day 5 visit. Similarly, the Day 29 summary will denote the number of patients with stenosis events that occurred after Day 5, and up to Day 29 (inclusive of Day 29).

The time of first stenosis (in days) will be summarized and calculated as number of days from HAV implantation to date of first stenosis event: Date of Stenosis – Date of Day 1 + 1. Patients who did not have a stenosis event will not contribute a value for this summary.

Please note, the clinical duplex will be recorded for all visits. Results after Month 12 **will not** be summarized in tables and will be provided in the listings.

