5.4 Safety Laboratory Parameters

Clinical laboratory variables will be described using summary statistics for the actual values at each visit, as well as for the absolute change from baseline to each visit. The standard error of the mean (SEM) will be included in these tables.

The following laboratory parameters were determined and will be described for the corresponding visits:

Hematology (measured at screening and Month 6)

- Hemoglobin
- Hematocrit
- Red Blood Cells (RBC)
- Absolute Lymphocytes
- Absolute Monocytes
- Absolute Eosinophil
- Absolute Basophil
- White Blood Cells (WBC)
- Absolute Neutrophil Count

Clinical Blood Chemistry (measured at screening and Month 6)

- Sodium
- Potassium
- Calcium

Final Analysis 19/23

- Blood Urea Nitrogen (BUN)
- Total Bilirubin
- Creatinine
- Glucose (non-fasting)
- Albumin

Coagulation (measured at screening and Month 6)

- International Normalized Ratio (INR)
- Activated Partial Thromboplastin Time (aPTT)

Immunology (measured at screening and Month 6)

• PRA sample collection date will be listed.

Hematology, chemistry and coagulation values are quantitative. The findings (normal, abnormal clinically significant [CS], abnormal not clinically significant [NCS]) are available for each test and will be provided in the listings.

The laboratory values were provided by local laboratories and unit values are not consistent across sites. The values used for the table summary will be **conventional units** and will be calculated by a conversion method.

6 Adverse Events (AEs)

Adverse events that started before HAV implantation are collected and documented in the EDC as medical history.

Adverse events will be coded by MedDRA. Presentation of adverse events will be the number of entries, as well as the number and percentage of affected patients. Tabulations will show numbers of adverse events by system organ class (SOC), preferred term (PT), and severity.

Each documented adverse event per patient will be considered, i.e. if a patient experienced the same adverse event (identical adverse event description) more than once during study duration, all events will be counted.

To give an overview of all adverse events a frequency table will be prepared showing the following information (displaying number of patients, percentage of patients and number of events).

Overview table:

- any AEs
- any serious AEs (SAEs)

Final Analysis 20/23

any AEs leading to death as outcome

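### The adverse event tables pool all events to the data cut with no Month 12 split and no patient-years, although full collection stops at Month 12 and planned follow-up at the 1-year analysis runs from 12 to 48 months

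*SAP*

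**What the plan says.** **Analysis.** SAP 3.4 takes all data available at extraction into the 1-year analysis and adds: "Event tables (such as concomitant medications, AEs), will include all events during the study". SAP 6 specifies the format: "Presentation of adverse events will be the number of entries, as well as the number and percentage of affected patients". Repeat events are all included; for a patient with the same event "more than once during study duration, all events will be counted". The tables of AEs, SAEs, severity, deaths and discontinuations follow this pattern. Protocol 9.2 adds no time window or patient-time denominator.

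**Collection.** Under Protocol 8.5, routine AE reporting ends at the Month 12 or early termination visit, apart from follow-up of unresolved AEs. Then: "During the long term follow up period from post Month 12 through Month 60, only the following will be reported by the investigator", namely all SAEs and all Events of Special Interest. Protocol 8.2 defines serious broadly and includes "any event involving the HAV that results in a surgical or endovascular radiological intervention".

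**Timing.** Protocol 4.3: "Enrollment (accrual) is expected to occur over 36 months". The 1-year analysis takes place when the last patient, or the last from the initial 36-month accrual, reaches 12 months.

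**Status of the endpoint.** Frequency and severity of AEs is a primary safety endpoint (Protocol 4.2.1, SAP 2.1). Protocol 2.5.3 plans to compare the study's data with historical data on synthetic bypass grafts.

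**What was not available.** Table shells, and the SAP version 2.0 text after the Section 9 heading. The absence of a split is judged on SAP 3.4, 6 and 7.

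**The concern.** One percentage column has to carry two different things.

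- **Change of collection rule.** Before Month 12 every AE can enter the table. Afterwards a non-serious AE enters only if it is an Event of Special Interest. The late part of the severity table therefore leans towards serious events by design. Anastomotic bleeding and significant local inflammation are primary safety items but are not on the Events of Special Interest list (Protocol 8.4), so as AEs they are captured after Month 12 only if serious. Because any event of the human acellular vessel (HAV) that leads to intervention counts as serious, this gap is confined to milder late events. It applies at the 1-year and the final analysis.
- **Unequal follow-up.** Aneurysm, pseudoaneurysm, spontaneous rupture, infection and removal are collected to Month 60. Their percentages at the 1-year cut average over patients followed for very different times. At the final analysis planned follow-up is equal, but dropout and death still make it uneven.

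What is at stake is interpretation. A historical comparison needs an incidence over a known window, or a rate; the pooled percentage is neither. The same 1-year report does use a Month 12 window elsewhere. For duplex stenosis, "The duplex ultrasound parameters will be summarized by planned visit up to Month 12", and time to loss of patency is reviewed for the first 12 months (SAP 4.4.4).

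**Working it through.** **Inputs.** Accrual 36 months and participation about 61 months (Protocol 4.3). Total duration 97 months (Protocol Summary). 15 patients recruited (SAP 1.5). Sister study CLN-PRO-V002 (Protocol 2.4.3): 13 of 20 completed 24 months; 13 of 20 had an SAE; primary assisted patency 63.2% at Month 12 and 57.9% at Month 24. Actual accrual dates are not given, so even entry over 36 months, or over 18 months as an alternative, is an assumption.

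**The plan's own figure.** 36 + 61 = 97 months, which reproduces.

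**Range at the 1-year cut.** Last patient 12 months; first patient 36 + 12 = 48 months.

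**Share of follow-up after Month 12.** Let t be planned follow-up in years, uniform on 1 to 4 (36-month accrual) or 1 to 2.5 (18-month).

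- No dropout: mean 2.5 years, so 1.5/2.5 = 60%. In 15 patients that is 22.5 of 37.5 patient-years. With 18-month accrual, 0.75/1.75 = 43%.
- Dropout at the sister study's rate, d = -ln(13/20)/2 = 0.215 per year, assumed constant and independent: expected time observed by t is (1 - exp(-dt))/d. This is 0.900 at t = 1, and averages 1.886 (36-month) or 1.444 (18-month). Shares: (1.886 - 0.900)/1.886 = 52%, or 14.8 of 28.3 patient-years; (1.444 - 0.900)/1.444 = 38%.
- Final analysis: 48/60 = 80% without dropout; (3.061 - 0.900)/3.061 = 71% with it.

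**Effect on a percentage.** Observed incidence by t is I(t) = integral from 0 to t of h k s^(k-1) exp(-h s^k) exp(-d s) ds. The pooled table shows the mean of I(t) over t; a 12-month table shows I(1). Shape k = 1 is a constant hazard; smaller k puts events early.

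*Any SAE*, h solved so that I(2) = 13/20, with dropout:

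| k | by Month 12 | pooled, 36-month accrual | excess of 15 | pooled, 18-month accrual | excess of 15 |
|---|---|---|---|---|---|
| 0.25 | 60.3% | 65.7% | 0.8 | 63.9% | 0.5 |
| 0.3 | 59.4% | 65.8% | 1.0 | 63.7% | 0.6 |
| 0.5 | 55.7% | 66.2% | 1.6 | 62.8% | 1.1 |
| 1 | 46.6% | 66.8% | 3.0 | 60.6% | 2.1 |

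Setting d = 0 gives larger values with 36-month accrual (1.2 at k = 0.25, 2.3 at 0.5, 4.4 at 1). That ignores the 7 of 20 early exits in the very study used for calibration, so I do not rely on it.

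*First HAV occlusion* (primary assisted patency as proxy): cumulative hazards -ln(0.632) = 0.459 and -ln(0.579) = 0.546 give k = ln(0.546/0.459)/ln 2 = 0.25. With 36-month accrual: 36.8% by Month 12 against 43.4% pooled without dropout; 35.5% against 40.1% with it. The excess is 1.0 and 0.7 patient.

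*Rare event*, assumed h = 0.05 (12-month incidence 4.9% without dropout), k from 0.3 to 1, 36-month accrual: pooled/12-month ratio 1.2 to 2.4, excess 0.1 to 1.0 patient.

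**Precision at n = 15.** Exact 95% intervals: 1/15, 0.2-31.9%; 9/15, 32-84%; 10/15, 38-88%.

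**The case against.** The strongest reply is that this is a declared choice. The safety endpoints carry no time point, endpoints are assessed over up to 60 months, and SAP 3.4 says openly that event tables run past Month 12. There is one arm, no hypothesis test and an exploratory label, so no between-arm bias or error rate is involved. All of this stands. A reader might infer that the tables break the plan or that an estimand is missed; the documents do not support that.

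A reader might also infer that late safety information is lost. It is not. SAEs and Events of Special Interest are collected to Month 60. The HAV site is examined at each long-term visit (Protocol 7.5.4), vascular examinations are listed (SAP 4.4.4), and the final analysis has a physical examination shift table (SAP 5.2). The split can be rebuilt from the listings, patients per visit (SAP 4.1), complication onset (SAP 6), study duration (SAP 7.1) and the AE onset days that SAP 7.2 provides for. With 15 patients that is feasible by hand.

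Three further readings go too far:

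- That no footnote will explain the change of rule: this cannot be checked without the table shells.
- That every other outcome is cut at Month 12: interventions are also tabulated throughout the study (SAP 4.4.2), and the Kaplan-Meier patency curves have no such limit (SAP 4.4.1).
- That three of 15 is a typical excess: with the sister study's dropout it needs a constant SAE hazard after surgery and full 36-month accrual. At k = 0.25, the shape fitted to the sister study's patency, it is 0.8. Not all SAEs are occlusions, so that shape is itself an assumption.

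The objection that a post-Month 12 rate would be imprecise is also right. One event in 14.8 patient-years is 6.8 per 100, exact 95% CI 0.2 to 37.6.

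What survives is that none of the AE tables specified gives an incidence over a fixed window under one collection rule.

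**Conclusion.** The point holds as a worthwhile, inexpensive improvement, not as an error that invalidates an analysis. As specified, the AE frequency and severity tables mix two collection rules at both analyses. Percentages for events collected to Month 60 rest on unequal follow-up: 12 to 48 months by plan at the 1-year cut and, less so, through dropout and death at the final analysis. The cumulative tables are permitted, but they supply nothing directly comparable with the historical data named in Protocol 2.5.3.

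On size, 38-60% of follow-up at the 1-year cut falls after Month 12, assuming even accrual over 18 to 36 months and either no dropout or the sister study's rate. With that dropout rate, the excess over 12-month incidence is about 0.5 to 2 patients of 15 for any SAE. For first occlusion and for rare events it is about one patient or fewer. All of this is small against the exact intervals at n = 15. The patient counts depend on assumed hazard shapes, and the dropout is assumed independent although four of the sister study's seven early exits followed occlusion. The change in collection rule depends on none of these assumptions.

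**What to change.** In SAP 3.4 and 6:

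- Add a table of AEs and HAV complications from implantation to the Month 12 visit.
- Add a separate post-Month 12 table of SAEs and Events of Special Interest, with patient-years. A rate per 100 patient-years is optional, given its imprecision.
- Keep the cumulative tables, with a footnote that only SAEs and Events of Special Interest are collected after Month 12.

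Patient-years alone would not be enough. Under even 36-month accrual without dropout, dividing non-serious AEs by all patient-years would understate their rate by 60%, since 15/37.5 = 0.40. The split is needed first.

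The cost is one extra set of tables and a footnote, from event dates and study duration already collected.

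A separate editorial matter, which adds no weight here: Protocol 7.2 lists only HAV-associated SAEs in long-term follow-up, while Protocol 7.5.4, 8.5, 8.5.5 and Appendix 1 footnote 7 set no relatedness limit. Those passages must be reconciled.
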